12.3. REGISTRATION ELIGIBILITY WORKSHEET

At the time of registration, the information requested on the On-Study/Eligibility Worksheet Form will be completed by the Study Coordinator and reviewed by the PI.

12.4. DATA COLLECTION FORMS AND SUBMISSION SCHEDULE

All data will be collected using USC CISO data collection forms. The original data collection forms will reside at USC in secure location.

- Within two weeks of registration, the data manager will complete the On-Study Form (Form OS).
- Within two weeks of completion of each course of treatment, the data manager must complete the following:

Treatment and Adverse Event Form

Supplemental Data Form (if applicable)

Flow Sheets (These are to be submitted along with each treatment form.)

Each time a patient is evaluated for response and/or new follow-up information is obtained the data manager will complete the Response/Off-Study/Follow-Up Form.

13.0 STATISTICAL CONSIDERATIONS

Study Design: This is a two-stage, single arm study to obtain preliminary evidence of efficacy of Eribulin in the treatment of recurrent cervical cancer. Current chemotherapy treatments for recurrent cervical cancer are associated with response rates and 6-month progression-free survival rates no higher than 10%. The objective of this study is to determine whether there is evidence that treatment with Eribulin will result in response and 6-month PFS rates that exceed 10%, suggesting promising activity and encouraging further study.

The primary efficacy endpoint will be 6-month progression-free survival (PFS₆). The secondary efficacy endpoint will be best overall response (BOR). A total of 30 patients who are fully evaluable for PFS₆ will be enrolled on this study. Patients who are not fully evaluable for PFS₆ will be replaced. Replaced patients will nonetheless be included in the final efficacy analysis. PFS₆ will be the endpoint for interim monitoring.

An interim analysis will occur when 15 patients have been evaluated for PFS₆, with final analysis once 30 patients have been evaluated for PFS₆. $\geq 1/15$ patients who achieve PFS₆ are required to continue study accrual to 30 patients. $\geq 6/30$ patients who achieve PFS₆ will be considered sufficient evidence of efficacy to warrant further study. The study will be terminated if fewer than 1/15 patients are progression-free at 6 months. The study may remain open pending the interim results on the first 15 patients, but will be suspended to enrollment if the 20th patient is enrolled before the interim results are available.

Sample size justification. This design has one-sided Type I error of <0.10 (0.072) for a true PFS₆ rate of 10%, and power of at least 0.80 for a true PFS₆ rate of 26%. Hence this study has sufficient power to detect moderate and clinical important improvements in PFS₆ rate due to Eribulin treatment when compared to past experience with chemotherapy treatment of recurrent cervical cancer.

Additional efficacy analyses. Product limits estimates of 6-month PFS will be computed using all patients enrolled on the study. 95% confidence intervals will be based on Greenwood standard errors. In addition, exact 95% binomial confidence intervals will be compute for the BOR rate.

Toxicity analyses. The rate of Grade 3+ hematology and non-hematologic toxicities will be computed for course 1 and for all courses combined.

Interim Monitoring of Toxic Death. The occurrence of toxic death (TD) at any time will be a primary endpoint for safety monitoring. A population TD rate that exceeds $p=0.05$ will be considered unacceptable. Monitoring will be based on a Bayesian rule on the binomial frequency of TD using a Beta(1,3) prior. A posterior probability of $\geq 90\%$ that the population TD rate p exceeds 0.05 will be sufficient to require that the cause and circumstances of the TDs be reviewed immediately with the study committee and with the Data and Safety Monitoring Committee to determine whether modifications to or termination of the study are warranted. Operationally this will occur if 1 TD occurs within the first 8 patients, or 2 occur

within the first 19 patients. A posterior probability of $\geq 97.5\%$ that p exceeds 0.05, with the occurrence of at least 2 TDs, will be considered very compelling evidence that the population toxic death rate exceeds 5%, and will require immediate termination of the study unless a convincing rationale for continuing the study exists. Operationally this will occur when 2 TDs within the first 10 patients, 3 within the first 19, or 4 during the study are observed.

Analysis of correlative endpoints. The analysis of GRP78 IHC score and GRP78 serum level, as well as other correlative markers (e.g. Tau-protein, alpha- & beta-tubulin), will be analyzed via Cox regression analysis for PFS, and via logistic regression for BOR rate. The power of these analyses is difficult to determine, since there is little preliminary data on the distribution of these endpoints in tumor and serum. However, the power of these analyses can be appreciated from the following. If, for example, GRP78 IHC level is divided at the median, and BOR rate is 25% with Eribulin in this population, there will be 73% power to detect a difference in BOR rate of 5% vs 45% in the two resulting group, based on a two-sample two-sided test of proportions with 5% Type I error. Hence it is likely that only profound associations between measures of efficacy and levels of GRP78 and other correlative endpoints will be detectable. Actually analyses based on ordered categorical and continuous measures will be somewhat more powerful than this. Similar considerations apply to the other correlative endpoints that will be studied.

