8.3 TREATMENT REMOVAL

Patients will be removed from treatment in the event of:

- Peripheral neuropathy Grade >2 that does not improve as in Section 8.1
- Grade 3 or 4 hypersensitivity/infusion reaction.
- Inability of subject to comply with study requirements.
- Determination by the investigator that it is no longer safe for the subject to continue therapy.
- Progression of disease (as defined in Section 10.1).
- Delay of treatment \geq 2 weeks.
- Patient may choose to withdraw her participation at any time for any reason

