History & Physical Exam	X	X			X	
Weight, Performance Status	X	X				
Toxicity Assessment		X Day 1 and 8				
WBC (differential), Hgb, platelets	X	X Day 1 and 8				
Electrolytes, MG, BUN, Cr	X	X				
LFT (Bilirubin, AST, ALT, Alkaline phosphatase		X				
EKG	X			X		
CXR	X		X ⁶			
Radiology, x-ray or Scans for disease measurement	X		X			
Tissue collection ³	X					
Peripheral Blood Collection for Correlative Studies		X ⁴				X
Eribulin		Day 1 and 8				

¹ Within 24 hrs² As clinically indicated³ From paraffin embedded prior biopsy⁴ Cycles 1-6⁵ Within 28 days of each cycle⁶ CXR is only required in the event that a CT of the chest is not done. Should a CXR be given in place of a CT scan, an additional CXR should be repeated every 2 cycles.

10.0**CRITERIA FOR EVALUATION AND ENDPOINT DEFINITIONS**

The outcome status (in terms of toxicity, response, reason off study, progression, and survival) of all eligible patients will be reported. All eligible patients who begin treatment will be included in the analysis of response, survival and time-to-failure.

Toxicities and adverse events including laboratory adverse events will be graded and summarized according to the National Cancer Institute CTCAE, v4.3 (available on the NCI website at: <http://ctep.cancer.gov/forms/CTCAEv4.pdf>).

Response will be evaluated according to the RECIST criteria v1.1:

Eligibility

Only patients with measurable disease (at least one measurable lesion) at baseline should be included in protocols where objective tumor response is the primary endpoint.

Measurable lesions - lesions that can be accurately measured in at least one dimension with longest diameter ≥ 10 mm and 2x slice thickness on CT scan. Lymph nodes must be ≥ 15 mm in **short axis**. Bone lesions may be measurable if there is a lytic/soft tissue component that meets minimum size criteria. CXR lesions must be > 20 mm.

Non-measurable lesions - all other lesions, including small lesions or lesions not conventionally measurable (i.e. leptomeningeal disease, ascites, pleural/pericardial effusion, inflammatory breast disease, lymphangitis cutis/pulmonis, cystic lesions, and also abdominal masses that are not confirmed) should be noted and followed by imaging techniques but not measured.

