- Patients with a global deterioration of health status requiring discontinuation of treatment without objective evidence of disease progression at that time should be classified as having “symptomatic deterioration”. Every effort should be made to document the objective progression even after discontinuation of treatment.
- In some circumstances it may be difficult to distinguish residual disease from normal tissue. When the evaluation of complete response depends on this determination, it is recommended that the residual lesion be investigated (fine needle aspirate/biopsy) to confirm the complete response status.

Confirmation

- The main goal of confirmation of objective response is to avoid overestimating the response rate observed. In cases where confirmation of response is not feasible, it should be made clear when reporting the outcome of such studies that the responses are not confirmed.
- To be assigned a status of PR or CR, changes in tumor measurements must be confirmed by repeat assessments that should be performed no less than 4 weeks after the criteria for response are first met. Longer intervals as determined by the study protocol may also be appropriate.
- In the case of SD, follow-up measurements must have met the SD criteria at least once after study entry at a minimum interval (in general, not less than 6-8 weeks) that is defined in the study protocol

Duration of overall response

- The duration of overall response is measured from the time measurement criteria are met for CR or PR (whichever status is recorded first) until the first date that recurrence or PD is objectively documented, taking as reference for PD the smallest measurements recorded since the treatment started.

Duration of stable disease

- SD is measured from the start of the treatment until the criteria for disease progression are met, taking as reference the smallest measurements recorded since the treatment started.
- The clinical relevance of the duration of SD varies for different tumor types and grades. Therefore, it is highly recommended that the protocol specify the minimal time interval required between two measurements for determination of SD. This time interval should take into account the expected clinical benefit that such a status may bring to the population under study.

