10.1 ENDPOINT DEFINITIONS

10.1.1 PRIMARY EFFICACY ENDPOINT

Progression-free survival is defined as the time from first day of treatment to the first observation of disease progression or death due to any cause. If a patient has not progressed or died, progression-free survival is censored at the time of last follow-up.

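### Does replacing patients who are not evaluable for 6-month PFS undermine the stated type I error and power?

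*Combined protocol and SAP*

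**What the plan says.** Section 13.0 states that "The primary efficacy endpoint will be 6-month progression-free survival" and enrols until 30 patients are fully evaluable for it. Those who are not "will be replaced. Replaced patients will nonetheless be included in the final efficacy analysis". The cut-offs are at least 1 achiever among 15 to continue and at least 6 among 30 to declare the drug worth further study. On error control it says "This design has one-sided Type I error of <0.10 (0.072" for a true rate of 10%, with power of at least 0.80 at 26%. Under its additional efficacy analyses it adds: "Product limits estimates of 6-month PFS will be computed using all patients enrolled on the study".

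Three other places bear on the point:

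- Section 10.0: "All eligible patients who begin treatment will be included in the analysis of response, survival and time-to-failure".
- Section 10.1.1 makes progression or death from any cause a PFS event. Otherwise: "If a patient has not progressed or died, progression-free survival is censored at the time of last follow-up".
- Section 10.0 sets apart, as symptomatic deterioration, a decline in health "requiring discontinuation of treatment without objective evidence of disease progression at that time", and asks that progression still be documented after treatment stops. Section 8.3 also allows that "Patient may choose to withdraw her participation at any time for any reason".

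**The concern.** The decision turns on a handful of patients, and the plan lets treated patients leave the counted set after part of their course is known. Three things are unwritten: what makes a patient evaluable, how many may be replaced, and how a replaced patient enters the 1/15 and 6/30 counts. The natural reading is that 30 evaluable patients decide and that replaced patients appear only in the all-patient product-limit estimate, which carries no go/no-go rule.

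On that reading the stated error rates need evaluability to be unrelated to outcome. A patient who deteriorates without measured progression and is then lost is probably a failure, yet she would be censored and could be replaced. If that were common, the evaluable patients would do better than the treated population and the false-positive rate would rise above the plan's 0.10 ceiling. If instead patients who were doing well withdrew, power would fall.

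**Working it through.** **Inputs from Section 13.0.** Stage 1 has 15 patients and continues with at least 1 achiever; the total is 30 and success is at least 6; null rate 0.10; alternative rate 0.26. The documents give no non-evaluable rate, so the values of *f* and *g* below are assumptions.

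**Reproducing the stated figures.** The probability of a positive result at rate *p* is

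A(p) = Σ (x = 1 to 15) b(x; 15, p) × P[Bin(15, p) ≥ 6 − x].

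- A(0.10) = 0.0727; the plan prints 0.072.
- A(0.26) = 0.828; the plan says at least 0.80.

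Both are right for 30 counted patients who have the stated true rate.

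**Replacement unrelated to outcome.** The rate among evaluable patients equals the population rate, so 0.0727 and 0.828 are unchanged however many are replaced.

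**Every replaced patient a failure.** If a fraction *f* of treated patients is replaced, the evaluable rate under the null is 0.10/(1 − f), and the expected number of replacements per 30 evaluable is 30f/(1 − f).

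| f | Replaced per 30 evaluable | Evaluable rate | Type I error |
|---|---|---|---|
| 5% | 1.6 | 0.1053 | 0.089 |
| 10% | 3.3 | 0.1111 | 0.108 |
| 15% | 5.3 | 0.1176 | 0.133 |

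Solving A(p) = 0.10 gives p = 0.1088. Then f = 1 − 0.10/0.1088 ≈ 0.0805, or about 2.6 replacements per 30 evaluable.

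**Replaced patients at half the others' success rate.** The evaluable rate is 0.10/(1 − f/2). Type I error is 0.080, 0.089 and 0.098 at f = 5%, 10% and 15%, and reaches 0.10 at f ≈ 0.161.

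**Only would-be achievers lost.** If those lost equal a fraction *g* of all patients, the evaluable rates are (0.10 − g)/(1 − g) and (0.26 − g)/(1 − g). At g = 5%, type I error is 0.004 and power 0.677. That case loses 0.05/0.10 = half of all achievers under the null and 0.05/0.26 = 19% under the alternative, with no failure lost. Power reaches 0.80 at g = 0.0116, or 0.0116 × 30 ≈ 0.35 of a patient in 30.

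**The alternative rule: first 30 treated, unknown status counted as not achieved.** The counted rate cannot exceed the true rate, so type I error is at most 0.0727. Power depends on what 26% describes:

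- If it is the rate in all treated patients with unknowns already counted as failures, power stays 0.828.
- If it is the rate in assessable patients and loss is unrelated to outcome, the counted rate is 0.26(1 − f). Power is 0.785 at f = 5% and 0.734 at f = 10%. It passes below 0.80 at f ≈ 0.0334, and 0.0334 × 30 ≈ 1 patient.
- If achievers equal to 5% of patients are lost, the counted rate is 0.26 − 0.05 = 0.21 and power is 0.623, against 0.677 under replacement.

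**The case for a change.** The strongest case for a change is that two or three patients can settle a 6-of-30 decision in an open-label single-arm trial, so their handling should be fixed before their outcomes are known. Unassessable status in advanced cancer is plausibly linked to failure. The all-patient product-limit estimate neither drives the decision nor escapes the problem, since it also assumes uninformative censoring. The other reading offers no shelter either: if replaced patients with the population rate were added and the cut-off stayed at 6, type I error would be 0.083, 0.105 and 0.129 with 1, 3 and 5 extra patients.

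Much of this stands as a description. The term is undefined, and a written sentence would have been better. But the last reading needs a known 6-month status for patients who were replaced because, on the ordinary meaning of the term, they had none. Scaling the cut-off to 20% of 30 + m (7 achievers) points the other way: type I error is 0.031, 0.042 and 0.055 for m = 1, 3 and 5, with power 0.731, 0.791 and 0.839. The text does not select a reading that breaks the error ceiling.

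The route to replaced failures is also narrow. Documented progression or death before 6 months is an event, hence an assessed failure. Section 10.0 asks for every effort to document progression after symptomatic deterioration, and the Section 9.0 calendar appears to schedule follow-up every 3 months for 2 years (the table is broken in the text available). A replaced failure needs deterioration or withdrawal, no documented progression and no known death by 6 months. That can happen, but nothing in the documents points to 8% or more of patients. Nor do Sections 10.0 and 13.0 conflict: the first names who enters the response, survival and time-to-failure analyses and sets no denominator for the 6/30 rule.

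**Conclusion.** No change to the plan follows. No stated figure is wrong; the type I error and power are correct for 30 counted patients and survive any amount of replacement that is unrelated to outcome. Passing the 0.10 ceiling takes about 8% replaced with every one a failure; at 10% replaced the excess is 0.108 against 0.10.

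The missing definition is a gap that an analyst fills sensibly from Section 10.1.1: progression or death before 6 months is a failure, and only unknown status makes a patient unevaluable. Writing that down adds detail without altering the design. Moving the decision to all treated patients is a real alternative, but it gives up an openly stated replacement rule, secures type I error and not power, and may breach the plan's own 0.80 with one unassessable patient in 30. A sponsor's statistician could reasonably prefer either.

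This rests on two assumptions: that analysts read evaluability from the PFS definition, so documented failures are not replaced, and that unknown 6-month status is uncommon or only partly linked to failure. If reports showed three or more replacements, most of them after clinical decline, the 6/30 result should be read with the all-patient estimate beside it.

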15.2 DATA SAFETY AND MONITORING COMMITTEE

The *Data and Safety Monitoring Committee (DSMC)* at the USC Norris Comprehensive Cancer Center (NCCC) is an independent body and is responsible for the safety of study subjects through the review of new protocols to ensure an adequate adverse event reporting plan and through the real-time and periodic

monitoring of severe adverse events (SAEs) or those that require expedited reporting. The DSMC also performs real-time, quarterly and annual study progress and safety review, as well as efficacy/futility review as outlined in the NCCC Data and Safety Monitoring Plan (available upon request). After each review, the DSMC reports the results of each review and make recommendations to the study PI, IRB, and C/C.

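### The printed toxic-death review counts leave out a third death reached at patients 20 to 30, although the plan's own 90% posterior rule requires review there

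*Combined protocol and SAP*

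**What the plan says.** Section 13.0, under Interim Monitoring of Toxic Death, sets the event and the period: "The occurrence of toxic death (TD) at any time will be a primary endpoint for safety monitoring". The tolerance is "A population TD rate that exceeds $p=0.05$ will be considered unacceptable", and the method is "Monitoring will be based on a Bayesian rule on the binomial frequency of TD using a Beta(1,3) prior".

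There are two tiers.

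- **Review.** A posterior probability of at least 90% triggers this tier: "that the population TD rate p exceeds 0.05 will be sufficient to require that the cause and circumstances of the TDs be reviewed immediately". The reviewing bodies are the DSMC and the study committee, which decide whether the study is modified or ended. No minimum or maximum number of deaths is attached. The counts given are: "Operationally this will occur if 1 TD occurs within the first 8 patients, or 2 occur" by patient 19.
- **Termination.** This needs a posterior of at least 97.5% and at least two deaths. The counts given are: "Operationally this will occur when 2 TDs within the first 10 patients, 3 within the first 19, or 4 during the study are observed".

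The planned size is 30 patients evaluable for 6-month PFS. Non-evaluable patients are replaced, and no upper limit on enrolment is stated.

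**The concern.** The termination list ends with an entry that runs to the end of the study. The review list has no such entry; its last count expires at patient 19. Yet the review rule is the looser of the two and is meant to operate throughout.

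A cumulative third death reached at patients 20 to 30 is too late for every printed review count and one death short of the open-ended termination count. If the 90% rule is met there, rule and list give opposite answers on whether review is mandatory. In practice the counts are what study staff will apply. On the affected paths the first printed trigger is the fourth death, already at the termination tier, so the graded warning step is skipped.

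**Working it through.** **Inputs, all from Section 13.0.** Prior Beta(1,3); unacceptable rate above 0.05; review at posterior ≥ 0.90; termination at posterior ≥ 0.975 with at least two deaths; 30 patients.

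**Formula.** With x deaths in n patients the posterior is Beta(1 + x, 3 + n − x), and the monitored quantity is P(p > 0.05) = 1 − F(0.05; 1 + x, 3 + n − x), where F is the beta distribution function.

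**Step 1: reproduce the printed counts.**

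| Printed count | Posterior | One patient later |
|---|---|---|
| Review, 1 in 8 | 0.898 | 0.882 |
| Review, 2 in 19 | 0.905 | 0.895 |
| Termination, 2 in 10 | 0.9755 | 0.970 |
| Termination, 3 in 19 | 0.978 | 0.974 |
| Termination, 4 in 30 | 0.977 | 0.974 |

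Four of the five are exact cut-offs. The fifth, 1 in 8, is 90% only after rounding (1 in 7 gives 0.914). It errs towards more review and is not part of this point. The formula is therefore the one the plan used.

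**Step 2: evaluate the missing count, x = 3.**

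| n | 20 | 25 | 30 | 32 | 33 |
|---|---|---|---|---|---|
| Posterior | 0.974 | 0.951 | 0.919 | 0.904 | 0.896 |

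From n = 20 to 30 every value is at least 0.90, so review is required, and below 0.975, so termination is not. The rule holds for three deaths through n = 32.

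**Step 3: how often this matters.** A first review is missed only with no death in patients 1 to 8, at most one by patient 19, and a cumulative third by patient 30. Patients 9 to 19 and 20 to 30 are 11 each, so

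P(missed) = Σ over a = 0, 1 of (1 − p)^8 × P[Bin(11, p) = a] × P[Bin(11, p) ≥ 3 − a].

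At p = 0.10:

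- a = 0: 0.4305 × 0.3138 × 0.0896 = 0.0121
- a = 1: 0.4305 × 0.3835 × 0.3026 = 0.0500
- total: 0.0621

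A patient-by-patient recursion over n = 1 to 30 gives the same totals and splits them:

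| True TD rate | 5% | 10% | 15% |
|---|---|---|---|
| Rule met, printed review never fires | 2.8% | 6.2% | 5.5% |
| of which neither printed tier fires | 2.4% | 4.5% | 3.2% |
| of which first printed action waits for the fourth death | 0.4% | 1.7% | 2.3% |
| No printed review through patient 19 | 59.6% | 30.0% | 13.4% |
| Chance of the uncovered third death, given the row above | 4.7% | 20.7% | 41.0% |

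The last row is the first row divided by the fourth, for example 0.0621 / 0.3002 = 0.207.

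**Step 4: replacements.** If replacements take enrolment to 32 (an assumption), the first row becomes 3.9%, 8.1% and 6.7%, and the second 3.2%, 5.4% and 3.5%.

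**The case against.** The strongest reply is that the posterior rule is the governing instruction and the counts only translate it. Anyone who computes the posterior at a third death would hold the review, so the fault is an incomplete list and not an absent safety rule. That is true, but the counts are offered as the working form of the rule, and a reader who relies on them gets the wrong answer.

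Second, the affected paths are few. At a true rate of 10% a third death falls at patients 20 to 30 in 29.4% of trials by any path (running the recursion to 30 patients without stopping for termination). In about 23 of those 29 points a printed review has already fired. This stands, and it is why the unconditional figures should lead. The conditional figures apply only to trials with no printed review by patient 19. The 5% column is also the boundary of the tolerance, since only a rate above 0.05 is called unacceptable.

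Third, other oversight remains. Any death is a serious adverse event reported under Section 8.5, and Section 15.2 says "The DSMC also performs real-time, quarterly and annual study progress and safety review". This limits the harm. It is not the specific immediate review on modification or termination that Section 13.0 requires.

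Fourth, the plan does not say whether the first 19 patients are counted as enrolled, treated or evaluable, or how a late death in an early patient is placed. If such a death is placed at that patient's own enrolment position, it could still meet the patient-19 count after patient 20 has entered. This stands as a condition on the path probabilities, though not on the posteriors.

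**Conclusion.** The review counts are wrong as written against the plan's own rule. Three toxic deaths among 20 to 30 patients give a posterior between 0.974 and 0.919, which requires review, and neither printed list contains that event. The posteriors rest only on the stated prior, threshold and tolerance.

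The absolute size is modest: over 30 patients a required review is not triggered by the printed review counts in about 3% to 6% of trials at true rates of 5% to 15%. These frequencies assume independent deaths at a constant rate, with each patient's outcome known in order of entry. The consequence is nonetheless serious, because the event is a third treatment-related death, and the list says nothing where the rule says review is mandatory.

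**What to change.** In Section 13.0, add 'or 3 during the study' to the printed review counts. This introduces no new threshold; it applies the stated 90% rule.

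Three notes should go with it:

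- The added count follows the rule through 32 patients (0.904) but not at 33 (0.896). Because non-evaluable patients are replaced, the count would need rechecking if enrolment passes 32.
- The count of 1 in the first 8 can stay, with a remark that its posterior is 0.898, or 90% after rounding.
- The termination counts can stay for 30 patients. At 31, four deaths give 0.974, marginally below 97.5%.

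It would also help to state how patients are numbered for these counts.

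The cost is one clause and some additional reviews:

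| True TD rate | 2% | 5% | 10% | 15% |
|---|---|---|---|---|
| Chance of review, as printed | 16.6% | 40.4% | 70.0% | 86.6% |
| With the added clause | 17.0% | 43.2% | 76.2% | 92.1% |

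Sample size, the efficacy design and the termination tier are unchanged.
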